5.3 Exclusion Criteria

- 1. Unable to give consent
- Children age < 18 years and adults > 100 years old
- 3. Pregnant patients
 - As per standard of care, female patients of child-bearing age will have a urine pregnancy test prior to their procedure.

5.4 Withdrawal criteria

The research protocol will be terminated early if

- 1. Patients lose their capacity to consent or become clinically unstable
- 2. The patient chooses to withdraw from the study
- 3. The sponsor, the chief investigator or the research team review the data and decide to stop the study

5.5 Consent

Patients will be identified by members of their direct care team when they attend clinic appointments or are admitted as an inpatient to the hospital. Patient records may be reviewed to assess suitability and this will be performed by members of the direct care team. Participation in the study will be discussed with the patients by their direct care team and information will only be passed on to the research team with the patients consent. Verbal consent will be gained by the direct care team for personal contact information to be shared with the research team. This will be documented in the patient notes.

The direct care team will make patients aware that participation is voluntary and that if they do not wish to participate it will not affect their usual care.

Consent for the study of the prospectively recruited patients will be obtained by a member of the research team, this will be a physician who is experienced in performing conduction system implantation. Patients will have details of the study discussed with them and any family members or friends the patients wish to be present. They will also be provided with written information (patient information sheets). Patients will be given as much time as they wish, with a minimum of at least 24 hours, to decide whether they wish to participate in the study and will be offered additional visits to further discuss the study if they wish. Patients are able to withdraw their consent from the study at any time. Patients will be made aware that their participation is voluntary and that if they do not want to take part it will not affect their usual care. Patients who agree to take part in the study will sign a consent form, a copy of the form will be given to the patients and a second copy will be kept in their study record file. A copy will also be kept in the site file.

6 Adverse events

6.1 Definitions

Adverse Event (AE): any untoward medical occurrence in a patient or clinical study subject.

Serious Adverse Event (SAE): any untoward and unexpected medical occurrence or effect that:

- · Results in death
- Is life-threatening refers to an event in which the subject was at risk of death at the time
 of the event; it does not refer to an event which hypothetically might have caused death if
 it were more severe
- · Requires hospitalisation, or prolongation of existing inpatients' hospitalisation
- · Results in persistent or significant disability or incapacity
- Is a congenital anomaly or birth defect

Medical judgement should be exercised in deciding whether an AE is serious in other situations. Important AEs that are not immediately life-threatening or do not result in death or hospitalisation but may jeopardise the subject or may require intervention to prevent one of the other outcomes listed in the definition above, should also be considered serious.

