4.5 Burden/Risk

The main burdens for the patient include:

- The extra time taken to perform the experiments and experimental procedures during their scheduled clinical procedure due to the additional diagnostic investigations. The right heart electro-anatomical mapping will add 10 minutes. The echocardiography will add an additional 5 minutes.
- 2. The extra access in the groin for the mapping catheter and ICE catheter.
- 3. Patients receiving unconventional therapy with conduction system lead implantation

Control Group C: N=25 (Standard of care) I. 12-lead ECG Before the Echocardiogram procedure 3. MRI of the heart I. 12-lead ECG During the 2. Fluoroscopy procedure (x-ray) Routine clinical ca Follow-up 6 weeks, 6 months, 1 v Deleted:

The burden will be mitigated by the minimum extra time being used to complete the experiments, the use of local anaesthetic and the immediate removal of extra research related sheaths as soon as they are not needed

The main risks for the patient are:

A conduction system pacing wire is not known to have a higher complication rate compared to a conventional pacing wire. Conduction system pacing wires have been shown to be as effective as conventional pacing wires at preventing slow heart rates and improving heart pumping. If a complication occurs and the conduction system pacing wire cannot be implanted or does not perform as expected during follow-up a procedure will be performed to convert your pacing system to a conventional pacing system.

The additional risks of vascular tube placement include:

- 1% risk of bruising around the area
- 1 in 1000 risk of damage to the blood vessels requiring surgery
- Less than 1 in 500 risk of stroke

The additional risks of intracardiac echocardiogram include

- 1% risk of bruising around the access area in the leg
- Less than 1 in 1000 risk of heart perforation

The additional risks of electro-anatomical mapping include

Less than 1 in 1000 risk of heart perforation

Therefore, the overall risk of serious complications arising from taking part in the research study are less than 4 in 1000 (0.4%)

Pacemaker implantation involves exposure to ionising radiation to visualise lead implantation. Taking part in this study involves exposure to additional exposure to radiation above the standard clinical procedure due to the additional measurements that will be taken.

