4.6 Study Outcome Measures

Primary Outcome Measures

1. Success rates of conduction system lead implant (fluoroless workflow vs conventional methods)

Secondary Outcome Measures

- Procedure and fluoroscopy times of the fluoroless workflow vs current conventional methods of His-bundle and Left-bundle pacing
- Procedure and fluoroscopy times of the fluoroless workflow vs conduction system implant to current right ventricular pacing
- 3. Assess capture threshold of His-bundle and Left-bundle pacing from the fluoroless workflow vs that of conventional methods of conduction system implantation
- 4. Number of times leads deployed in the fluoroless protocol vs conventional methods of conduction system implantation
- Complication rates in the fluoroless protocol vs conventional methods of conduction system implantation:

- a. Lead implanted at the incorrect position: non-septal positions
- b. Lead displacement
- c. Lead injury
- d. Rise in threshold (late complication)
- e. Vascular injury
- f. Perforation with or without subsequent tamponade
- g. Device related infection
- h. Pneumothorax

5 Participant Entry

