6.2 Reporting Procedures

All adverse events should be reported. Depending on the nature of the event the reporting procedures below should be followed. Any questions concerning adverse event reporting should be directed to the Chief Investigator in the first instance.

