6.4 Serious AEs

An SAE form should be completed and faxed to the Chief Investigator within 24 hours. However, hospitalisations for elective treatment of a pre-existing condition do not need reporting as SAEs.

All SAEs should be reported to the "name of REC when allocated" where in the opinion of the Chief Investigator, the event was:

• 'related', ie resulted from the administration of any of the research procedures; and

• 'unexpected', ie an event that is not listed in the protocol as an expected occurrence

Reports of related and unexpected SAEs should be submitted within 15 days of the Chief Investigator becoming aware of the event, using the NRES SAE form for non-IMP studies. The Chief Investigator must also notify the Sponsor of all related and unexpected SAEs.

Local investigators should report any SAEs as required by their Local Research Ethics Committee, Sponsor and/or Research & Development Office.

Contact details for reporting SAEs

[contact]

[name] email: [contact]
Please send SAE forms to: [name].
[contact] (Mon to Fri 09.00 – 17.00)

7 Assessment and Follow-up

Patients will be followed up for a 1 year period. During this time they will undergo the device interrogation and wound check at 6 weeks as part of standard clinical care. One year after device implantation, patients will undergo a device interrogation follow-up appointment. Any incidental findings that we identify during the study will be reviewed by the research team and reported to the GP and also the cardiology team normally looking after the patient.

Definition of end of Study

The end of the study will be defined as completion of the 1 year follow-up of the 75 prospectively recruited patients for the invasive aspect of the study. This will be the date of the final visit of the last participant at 1 year.

8 Statistics and data analysis

The following statistical analysis has been reviewed and approved by our statistician, [name].

Power Calculations:

25 patients would provide the ability to determine the mean time of lead implantation of 120 minutes with a precision of (as a standard error) approximately \pm 10 minutes (assuming standard deviation of 47 min)⁷

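### The SAE definition in 6.1 includes unexpectedness, contradicting 6.4, and may keep serious anticipated complications off the 24-hour form

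*Protocol*

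**What the plan says.** Protocol section 6.1 defines an adverse event as "any untoward medical occurrence in a patient or clinical study subject", with no reference to expectedness. It defines an SAE as "any untoward and unexpected medical occurrence or effect that" meets one of the usual seriousness criteria. A closing paragraph lets medical judgement add further events: "Important AEs that are not immediately life-threatening or do not result in death or hospitalisation but may jeopardise the subject", or that may need intervention, are also to be treated as serious.

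Section 6.2 says "All adverse events should be reported", gives no time limit, and refers onward to the procedures that follow. Section 6.3 has non-serious events recorded whether or not they were expected.

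Section 6.4 gives the rule for SAEs: "An SAE form should be completed and faxed to the Chief Investigator within 24 hours". Its one stated exception is planned admission for a condition already present. It then sends to the ethics committee, within 15 days, those SAEs that are both related and unexpected, and requires the Chief Investigator to notify the sponsor of the same subset. Unexpected is explained there as "an event that is not listed in the protocol as an expected occurrence".

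Section 4.5 gives risks for the added procedures: vessel injury needing surgery, stroke, and, for both intracardiac echocardiography and mapping, "Less than 1 in 1000 risk of heart perforation". Section 4.6 lists eight complication types as secondary outcomes, including vascular injury and "Perforation with or without subsequent tamponade".

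**The concern.** Seriousness and expectedness are separate properties of an event. Section 6.1 merges them and section 6.4 separates them, so the definition does not fit the procedure built on it. Someone who follows 6.1 literally can conclude that a grave but anticipated complication is not an SAE and that the 24-hour form is not due.

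The study adds femoral access, electroanatomical mapping and intracardiac echocardiography to a pacemaker implant. The serious harms the protocol foresees from those steps are the ones described in 4.5. For a serious event regarded as expected, the 24-hour form is the only route with a deadline, because the 15-day report applies only to unexpected events. Section 5.4 allows the sponsor, the Chief Investigator or the research team to stop the study after reviewing data, and the protocol states no other timed flow of safety information for such events.

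**Working it through.** The check is logical; the only arithmetic concerns the likely number of events.

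**1. Compare the two rules.** Let S mean that a seriousness criterion is met, U that the event is unexpected, and R that it is related.

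| Step | As written | With U removed from 6.1 |
|---|---|---|
| SAE (6.1) | S and U | S |
| 24-hour form (6.4) | S and U | S |
| Ethics committee and sponsor (6.4) | (S and U) and R and U = S and R and U | S and R and U |

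As written, the second U does nothing. With the words removed, the ethics-committee and sponsor subset stays exactly the same. The only change is that events that are serious but expected gain the 24-hour form. The table leaves out the medical-judgement clause, which is taken up in step 3.

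**2. Which events are serious but expected?** This depends on a list the protocol does not label.

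- *Reading A:* the contents of 4.5 and 4.6 are the expected occurrences. This is the natural reading, since 4.5 quantifies the risks and totals them as serious complications. These events then fail U.
- *Reading B:* nothing is labelled as expected, so every event is unexpected. The 24-hour form then applies to every serious event, but the expectedness filter in 6.4 never excludes anything.

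**3. Trace a life-threatening tamponade under reading A.** It meets a seriousness criterion but is not unexpected, so it fails the main definition in 6.1. The medical-judgement clause carries no expectedness condition, but it is aimed at events that are not immediately life-threatening or do not end in death or hospitalisation. The *or* leaves its reach unclear, so it does not clearly bring this event back. Whether the event then falls by elimination into 6.3 or into no category, the result is the same: it is reportable under 6.2 without a deadline.

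**4. Trace a vessel injury needing surgery.** It also fails the main definition under reading A. The clause on events needing intervention may bring it back, unless it caused or prolonged hospitalisation, in which case coverage is again unclear.

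**5. Where each event is still counted.** Perforation with or without tamponade and vascular injury are complication items in 4.6. Stroke is not a 4.6 item, so it is captured only as an adverse event under 6.2.

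**6. Expected number.** Section 4.5 puts the overall risk of serious complications from taking part below 4 in 1,000. For the 25 + 25 = 50 derivation and validation patients, 50 × 0.004 = 0.2 events. The itemised figures add to 1 + 2 + 1 + 1 = 5 in 1,000, giving 50 × 0.005 = 0.25. Both assume that validation patients have all the added procedures, which 4.2 does not fix. The protocol gives no rates for complications of the implant itself, so these are extra and cannot be counted here.

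**The case against.** The strongest reply is that section 6, read as a whole, already intends the right rule. Section 6.4 ties the form to SAEs with one narrow exception and uses expectedness only for onward reporting, and 6.3 also treats expectedness as separate from seriousness. On that view the words in 6.1 are a slip. This stands as a statement of probable intent, but it also concedes that 6.1 contradicts 6.4.

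It can also be said that nothing in 4.5 or 4.6 is called expected, so no listed event is excluded (reading B). That is a tenable reading and limits the point: exclusion is a possible consequence, not a stated one.

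Three stronger readings are tempting, and the documents do not support them.

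- A reader might infer that none of the listed complications could ever generate a 24-hour form. The medical-judgement clause brings some in. Other 4.6 items, such as a non-septal lead position or a rise in threshold, may meet no seriousness criterion at all.
- A reader might infer that the events go unreported. Section 6.2 still requires all adverse events to be reported.
- A reader might infer that the test of the safety hypothesis in 1.2 is biased. The comparison rests on the 4.6 complication rates, not on an SAE count, and those events are counted whatever their SAE label.

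**Conclusion.** The definition in 6.1 is wrong as written because it contradicts 6.4. That part needs no assumption. The practical consequence is conditional: if the contents of 4.5 and 4.6 are treated as expected and 6.1 is followed literally, perforation with tamponade, stroke or surgically treated vessel injury may not trigger 24-hour notice to the Chief Investigator. Coverage is least certain for fatal and immediately life-threatening events.

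The effect is confined to reporting speed and the SAE tally. The primary outcome, sample size and complication-rate comparison are untouched. The number of events is likely to be small, but these are the events for which early notice matters most. The correction is worth making before recruitment relies on the current wording.

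**What to change.** 1. In 6.1, delete the words *and unexpected* from the SAE definition, so that an SAE is any untoward occurrence meeting a seriousness criterion.
2. In 6.4, keep *related* and *unexpected* solely as the filter for ethics-committee and sponsor reporting.
3. Add a short list stating which 4.5 and 4.6 events count as expected for that filter, and say that they still go on the 24-hour form when they meet a seriousness criterion.

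The cost is two words deleted, a short list and sentence added, and a few more SAE forms in a 75-patient study. The change secures notice to the Chief Investigator only. Because the 6.4 filter stays, expected SAEs would still not be among those the Chief Investigator must pass to the sponsor. If the sponsor wants them, that needs a separate sentence.

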6.2 Reporting Procedures

All adverse events should be reported. Depending on the nature of the event the reporting procedures below should be followed. Any questions concerning adverse event reporting should be directed to the Chief Investigator in the first instance.

6.3 Non serious AEs

All such events, whether expected or not, should be recorded.

6.4 Serious AEs

An SAE form should be completed and faxed to the Chief Investigator within 24 hours. However, hospitalisations for elective treatment of a pre-existing condition do not need reporting as SAEs.

All SAEs should be reported to the "name of REC when allocated" where in the opinion of the Chief Investigator, the event was:

• 'related', ie resulted from the administration of any of the research procedures; and

• 'unexpected', ie an event that is not listed in the protocol as an expected occurrence

Reports of related and unexpected SAEs should be submitted within 15 days of the Chief Investigator becoming aware of the event, using the NRES SAE form for non-IMP studies. The Chief Investigator must also notify the Sponsor of all related and unexpected SAEs.

Local investigators should report any SAEs as required by their Local Research Ethics Committee, Sponsor and/or Research & Development Office.

Contact details for reporting SAEs

[contact]

[name] email: [contact]
Please send SAE forms to: [name].
[contact] (Mon to Fri 09.00 – 17.00)

7 Assessment and Follow-up

Patients will be followed up for a 1 year period. During this time they will undergo the device interrogation and wound check at 6 weeks as part of standard clinical care. One year after device implantation, patients will undergo a device interrogation follow-up appointment. Any incidental findings that we identify during the study will be reviewed by the research team and reported to the GP and also the cardiology team normally looking after the patient.

Definition of end of Study

The end of the study will be defined as completion of the 1 year follow-up of the 75 prospectively recruited patients for the invasive aspect of the study. This will be the date of the final visit of the last participant at 1 year.

8 Statistics and data analysis

The following statistical analysis has been reviewed and approved by our statistician, [name].

Power Calculations:

25 patients would provide the ability to determine the mean time of lead implantation of 120 minutes with a precision of (as a standard error) approximately \pm 10 minutes (assuming standard deviation of 47 min)⁷

25 patients will provide the ability to determine the percentage of a successful implant with a precision of a SE (\pm 8%) of a success rate of approximately 80% SD of implant time = SD of total procedure time / $\sqrt{2}$ = 67 / $\sqrt{2}$ =47.37 SE = SD/ $\sqrt{\text{sample size}}$ = 47.37/ $\sqrt{2}$ 5 = 9.47

Data and all appropriate documentation will be stored for a minimum of 5 years after the completion of the study, including the follow-up period.

To assess the primary outcome of the success rates of the conduction system lead implant using the fluoroless workflow developed during our study, ECG information will be collected and capture will be determined by experts.

Fluoroscopy and procedural times will be analysed with one-way ANOVA. Success rates, capture thresholds and battery life will be analysed with t-test.

9 Regulatory issues

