4.2 Validation

25 patients will be recruited to the validation cohort.

An optimised work flow will be derived using the information collected from the derivation cohort. Namely, the target areas for FAM and electro-anatomical maps will be determined, and the successful pattern of lead septum interaction on CARTO will be defined.

The streamlined workflow will then be applied to 25 prospective patients. The success rates, procedure time, fluoroscopy time, capture threshold, number of attempted lead deployments and complication rates will be assessed.

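### Section 8 supports 25 per group with a time SE (9.47 min) for lead-implantation time, which is not an outcome (procedure time: 13.4 min), and gives no precision for the comparison with control

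*Protocol*

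**What the plan says.** Only the protocol was at hand, and the point concerns what its section 8 states.

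- **Time.** Section 8 says "25 patients would provide the ability to determine the mean time of lead implantation of 120 minutes with a precision of" about ±10 min, given as a standard error. It derives the SD from "SD of implant time = SD of total procedure time" divided by √2, that is 67/√2 = 47.37, and then 47.37/√25 = 9.47.
- **Success.** Section 8 says "25 patients will provide the ability to determine the percentage of a successful implant with a precision of a SE" of ±8%, at a success rate of about 80%.
- **Time outcomes.** The Study Summary lists fluoroscopy time and total procedure time. Section 4.6 lists "Procedure and fluoroscopy times of the fluoroless workflow vs current conventional methods of His-bundle and Left-bundle pacing". For the validation cohort, section 4.2 says "The success rates, procedure time, fluoroscopy time, capture threshold, number of attempted lead deployments and complication rates will be assessed". Section 8 plans the analysis: "Fluoroscopy and procedural times will be analysed with one-way ANOVA". None of these names lead-implantation time.
- **Comparison.** Section 3 recruits 25 controls so that success, procedure time, complications and fluoroscopy time can be compared. Section 4.6 words the primary outcome as "Success rates of conduction system lead implant (fluoroless workflow vs conventional methods"). The Study Summary words it without a comparator, and section 8 speaks of success "using the fluoroless workflow developed during our study".

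**The concern.** The two standard errors are the only support given for 25 patients per group, and they leave two gaps.

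1. The time precision belongs to a variable that is not an outcome. The SD of the variable that is an outcome, 67 min, is printed in the same calculation but is reduced by √2 before use. The reason for that step is not given. It would follow if procedure time were the sum of two independent parts of equal variance, but the protocol does not say so.
2. Both figures describe one group. A difference between two groups of 25 is estimated less precisely, and that difference is why the control arm is recruited.

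Someone who takes ±10 min and ±8% as the study's precision would expect tighter results than the design gives, both for procedure time and for the comparison with control.

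**Working it through.** **Inputs.** n = 25 per group (section 3). SD of total procedure time 67 min and success rate 80% (section 8). The protocol gives no arm-specific values, so equal values in both arms are an assumption. It gives no SD for fluoroscopy time, so nothing can be computed for that outcome.

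**The plan's own figures.**
- SD of implant time: 67/√2 = 47.38 (plan: 47.37, truncated).
- SE: 47.37/√25 = 9.47 min, as stated. With t(24) = 2.064, the 95% CI is ±19.5 min.
- Success: √(0.80 × 0.20/25) = 0.080, or 8 points, as stated.

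**One group, procedure time.**
- SE: 67/√25 = 13.4 min. 95% CI: 2.064 × 13.4 = ±27.7 min.
- Ratio: 9.47/13.4 = 0.71, so the stated SE is about 29% smaller than the one for the listed outcome.

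**Validation vs control, 25 vs 25.** For the same variable and equal spread, the SE of a difference is √2 = 1.41 times the one-group SE. Time intervals use t(48) = 2.011.

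| Assumption in both arms | SE of difference | 95% CI |
|---|---|---|
| SD 67 min | 67 × √(2/25) = 18.95 min | ±38.1 min |
| SD 53.6 min (20% lower) | 15.16 min | ±30.5 min |
| SD 80.4 min (20% higher) | 22.74 min | ±45.7 min |
| Success 80% | √(2 × 0.16/25) = 11.3 points | 1.96 × 11.3 = ±22 points |

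**Unequal success rates.** Section 1.1 quotes 95% and 56% as background rates. With validation at 80%:
- control at 95%: √((0.16 + 0.0475)/25) = 9.1 points (±18);
- control at 56%: √((0.16 + 0.2464)/25) = 12.7 points (±25).

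These show the range only. The normal approximation is poor at 95% with 25 patients, and the 56% comes from centres with new conduction system implanters.

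**A coincidence to avoid.** 13.4 min is also the two-group SE of implant time (47.37 × √(2/25) = 13.40). Here it is used only as the one-group SE of procedure time.

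**The case against.** The case for leaving section 8 alone has real substance.

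- **No stated figure is wrong.** Both quantities are named openly and called standard errors. Because the 67 min is printed, a reader can divide by 5 and reach 13.4. This stands, and it limits the weight of the point. It does not explain why the sizing rests on a variable that is never analysed.
- **One-group precision suits the aim.** The primary objective is to develop an implant protocol, and the Study Summary and section 8 word success without a comparator. The 8-point SE therefore stands for that reading. Sections 3 and 4.6 also plan a comparison, and for that no precision is given.
- **Time is a secondary outcome.** A protocol need not size every secondary outcome. That is true, but section 8 chose to cite a time precision, so it should be for the time outcome in use.
- **The √2 step may have a source.** The time sentence carries a reference marker, and that source is not at hand. The missing explanation therefore cannot be pressed. A source for the SD would still not make implant time an outcome.
- **The 25 vs 25 contrast and equal SDs are choices.** Section 4.5 adds mapping and echocardiography time in the study patients, so equal SDs are uncertain. ANOVA may also involve more than two groups. If derivation and validation were pooled (50 vs 25), the SEs would be 67 × √(1/50 + 1/25) = 16.4 min and √(0.16 × (1/50 + 1/25)) = 9.8 points, still above the one-group 13.4 min and 8 points.

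A reader might infer that the sample size calculation is miscalculated, or that the study is too small. The documents support neither. The arithmetic reproduces, sizing by precision is legitimate for a feasibility study, and the protocol states no target difference against which 25 per group could be judged too few.

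**Conclusion.** The point holds in a narrow form.

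- For procedure time, the protocol's SD gives a one-group SE of 13.4 min, against the 9.47 min quoted for implant time. This needs no assumption beyond the printed SD.
- The 8-point SE is valid for a single-cohort success rate and needs only a label.
- Neither figure is the precision of the comparison with control. Illustratively that is about 19 min (95% CI about ±38 min, or about ±30 to ±46 min if the SD is 20% lower or higher) and about 11 points (about ±22 points). These values assume validation vs control at 25 vs 25, with SD 67 min and 80% success in both arms.

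The weight is minor to moderate: the stated precision should be corrected, and the design is not called into question.

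**What to change.** Keep N=75 and reword the Power Calculations paragraph of section 8:

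1. State: *With 25 patients, mean procedure time (SD 67 min) is estimated with SE 13.4 min.* Keep the implant-time line only if lead-implantation time is made an outcome.
2. Label the 8-point SE as *single-cohort success rate*.
3. Add, marked as illustrative: *Assuming an SD of 67 min and 80% success in both arms, for validation vs control (25 vs 25) the difference in procedure time has SE about 19 min (95% CI about ±38 min; about ±30 to ±46 min if the SD is 20% lower or higher), and the difference in success rate has SE about 11 points (95% CI about ±22 points).*

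This serves both wordings of the primary outcome, since single-cohort and comparative precision are each given. It needs no extra patients and no change to procedures or analysis. The cost is that the stated precision looks less favourable and that the comparison figures rest on assumed equal SDs and success rates.
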